## The Study Protocol

The Coronavirus disease (COVID-19) pandemic has an enormous psychological impact worldwide (Luo et al., 2020). Individuals with suspected or confirmed COVID-19 have been defined as one of the most vulnerable groups suffering from psychological distress during the pandemic (Wang et al., 2020). In a study conducted with COVID-19 survivors, it has been found that this group had a significantly increased risk for developing psychiatric conditions such as anxiety and mood disorders, substance use disorders, and insomnia, even when comparing with other respiratory tract infections (Taquet et al., 2021). In addition, these psychiatric conditions remained elevated at the 6-month period for COVID-19 survivors. Therefore, COVID-19 survivors should be considered to be in need of an urgent intervention (Wang et al., 2020).

The proposed study aims to conduct a randomized controlled trial in order to implement culturally adapted cognitive behavioral intervention (CA-CBI) to COVID-19 survivors and evaluate the effectiveness of the intervention in reducing psychological distress for this particular group. Individuals who are 18 years or older, who got infected with COVID-19 and currently recovered, and who have a considerable amount of psychological distress will be included to the study. Individuals who have a severe mental disorder or suicidal risk will be excluded from the study. For screening purposes, an online survey followed by a structured interview will be conducted to identify the eligible participants. In the intervention part, CA-CBI will be implemented in a group format on Zoom which is an online platform with HIPAA compliance. For this purpose, the CA-CBI manual will be revised to the sample of COVID-19 survivors and the problems they are experiencing during the COVID-19 pandemic. Participants in the control group will receive online leaflets including a brief psychoeducation and appropriate referrals to receive free psychosocial support. To test the effectiveness of CA-CBI, all participants will be assessed one week before the intervention (pre-test), one week after the intervention (post-test), and one month after the post-test (follow-up). During the assessment, participants will be asked about psychological distress, symptoms of depression, anxiety, post-traumatic stress and somatization, as well as, questions about their quality of life, psychological flexibility and emotion regulation. The primary outcome is the psychological distress at the follow-up phase. A process evaluation will be conducted in order to assess the treatment fidelity and possible facilitators and barriers during the implementation of online-delivered group CA-CBI.

This project consists of 3 stages:

In the first stage, participants will be reached through social media and online communication channels and will be asked to fill out an online survey for screening purposes. Participants agreeing on the informed consent will be able to answer questions about demographics, COVID-19 related data (infection, recovery, etc.), psychological problems and suicidal risk. Participants who were infected with and recovered from COVID-19 will be able to continue with the Kessler-10 Psychological Distress Scale (K10). Those who score higher than 15 will continue to the suicidality questions. In this part, participants who are detected to have a suicidal risk will see a referral list on the screen where they can receive free psychological help for their suicidal ideations. Also, they will receive the phone number of the research team on the screen in case if they need to obtain more information about the referrals and to reach the research team. Participants who got infected with COVID-19 and recovered, who score a considerable amount of psychological distress ( $K > 15$ ), and who do not have a suicidal risk will be invited to the next stage of the screening procedure. In this

stage, the Structured Clinical Interview for DSM-5 (SCID-5) will be conducted with participants to screen any severe mental disorders. The structured interview will be conducted via Zoom and participants who have no severe psychiatric condition will be asked whether they would like to attend an intervention to decrease their psychological distress. After conducting SCID-5, eligible participants who agree to participate to the intervention will be included to the study and will be given the pre-test assessment one week before the intervention. Pre-test survey will take approximately 20 minutes. It is aimed that 86 participants who meet the inclusion criteria would participate to this phase of the study. The links of the surveys which will be created on Qualtrics will be shared on social media and online communication platforms. On these links, participants will first see the information about the study, and after giving consent to participate in the study, they will be able to complete the questionnaires.

In the second stage, eligible participants who agree to participate to the study will be randomly assigned to intervention (CA-CBI) group or control [enhanced treatment as usual (ETAU)] group. The required sample is identified as 86 participants for this stage. During the intervention, participants in the intervention group will receive online group CA-CBI for 8 weeks. Participants in the control group will receive a brief psychoeducation about their psychological distress as well as a referral list to consult appropriate places due to their psychological distress. In order to test the effectiveness of the CA-CBI for COVID-19 survivors, post-test assessment will be conducted with participants in the intervention and control group one week after the intervention. Participants in the control group will additionally be asked whether they received any psychological support during this process. To be able to observe the long-term effects of the CA-CBI, follow-up assessment will be conducted one month after the post-test. After all measures are completed, participants in the control group will be able to receive the intervention.

In the third stage, a process evaluation will be conducted to assess the treatment fidelity and the feasibility of implementation of the CA-CBI to COVID-19 survivors in an online group format. Interviews will be conducted with 5 completers, 5 drop-outs and 2 facilitators in order to evaluate the possible facilitators and barriers of attending/delivering the online group sessions.

The data will be analyzed by using a statistical package called IBM SPSS 26.0. The effectiveness of the intervention will be tested by comparing the changes in the scores of primary outcome measure (K10) and secondary outcome measures (PHQ-9, GAD-7, PCL-5, SCL-90-R Somatization subscale, WHOQOL BREF) between the baseline and follow-up measure. Mediation analyses will be conducted to explore the mechanisms of change by using the Psychological Flexibility Scale and Emotion Regulation Questionnaire.

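### CA-CBI is delivered in groups and ETAU is not, but the stated effectiveness analysis names no model and no therapy-group term; if run without one, standard errors are too small whenever outcomes correlate within groups

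*Combined protocol and SAP*

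**What the plan says.** All references are to the combined protocol and SAP, section The Study Protocol.

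- **Randomisation (second stage).** It is by individual: "eligible participants who agree to participate to the study will be randomly assigned to intervention (CA-CBI) group or control".
- **Intervention arm.** The overview says "CA-CBI will be implemented in a group format on Zoom". The second stage adds "participants in the intervention group will receive online group CA-CBI for 8 weeks".
- **Control arm (overview).** No group sessions are described: "Participants in the control group will receive online leaflets including a brief psychoeducation and appropriate referrals to receive free psychosocial support".
- **Effectiveness analysis (data analysis paragraph).** "The effectiveness of the intervention will be tested by comparing the changes in the scores of primary outcome measure (K10" and of five secondary measures, from baseline to follow-up. A software package is named, but no test, model or covariate.
- **Mediation (same paragraph).** "Mediation analyses will be conducted to explore the mechanisms of change by using the Psychological Flexibility Scale and Emotion Regulation Questionnaire". No group term is mentioned here either.
- **Sample size (second stage).** "The required sample is identified as 86 participants for this stage". No effect size, power, significance level or drop-out allowance is given.
- **Process evaluation (third stage).** "Interviews will be conducted with 5 completers, 5 drop-outs and 2 facilitators", so some drop-out is expected.

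The documents give no therapy-group size, number of groups, intraclass correlation (ICC) or design effect.

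**The concern.** Eight weeks of shared sessions, with the same fellow members and leader, can make outcomes within a CA-CBI group more alike than outcomes across groups. Randomising individuals does not remove this, because the correlation arises after allocation. It inflates the variance of the CA-CBI mean and leaves the ETAU mean unaffected.

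A comparison of changes that treats every CA-CBI participant as independent would then understate the standard error of the arm difference, and intervals would be too narrow. This applies to K10, to every secondary outcome, and to the arm-to-mediator step of the mediation analyses, which is the same two-arm contrast.

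With so few groups the ICC cannot be estimated reliably from the trial's own data. Whether to allow for group therefore has to be settled beforehand, and group membership has to be recorded as participants are assigned, including for those who later leave.

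**Working it through.** **Input from the documents.** Total randomised: 86.

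**Assumptions, none in the documents.** 1:1 allocation (43 per arm); 4 to 7 CA-CBI groups of near-equal size; equal total variance in both arms; two-sided 5% test; ICC of the change score 0 to 0.10. As a sensitivity case, 34 per arm analysed.

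**Step 1: the plan's own figure.** 86 cannot be reproduced, because its inputs are absent. Working backwards, 43 per arm with 80% power implies d = (1.960 + 0.842) × √(2/43) = 0.60 by the normal approximation, or 0.61 with the t distribution. This is a back-calculation, not a stated target.

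**Step 2: variance inflation of the arm difference.** With group sizes m_j and n per arm, let m' = Σm_j²/n. The CA-CBI mean has variance (σ²/n)[1 + (m' − 1)·ICC] and the ETAU mean has σ²/n. An unclustered test assumes 2σ²/n, so

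VIF = 1 + (m' − 1)·ICC/2, and actual type I error = 2[1 − Φ(1.96/√VIF)].

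Example with 4 groups of 11, 11, 11 and 10: m' = (3 × 121 + 100)/43 = 10.767. At ICC 0.10, VIF = 1 + 9.767 × 0.05 = 1.488 and √VIF = 1.220. Then 1.96/1.220 = 1.607, and type I error is 10.8%.

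| Groups (43 per arm) | VIF, ICC 0.05 | Type I | VIF, ICC 0.10 | Type I |
|---|---|---|---|---|
| 4 | 1.244 | 7.9% | 1.488 | 10.8% |
| 5 | 1.191 | 7.3% | 1.381 | 9.5% |
| 6 | 1.155 | 6.8% | 1.309 | 8.7% |
| 7 | 1.129 | 6.5% | 1.258 | 8.1% |

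At ICC 0 the error is 5.0%, and at ICC 0.01 it is 5.3-5.6%. With 34 per arm the ranges are 5.0%, 5.2-5.4%, 6.1-7.2% and 7.3-9.5% at ICC 0, 0.01, 0.05 and 0.10. Simulation of an unclustered t-test agrees to about 0.002.

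**Step 3: does allowing for group repair it?** The mean change in each CA-CBI group was compared with individual ETAU changes, using Satterthwaite degrees of freedom. Simulated type I error was about 5.0-5.8% in every setting (both sample sizes, all four ICCs, 4 to 7 groups). Median degrees of freedom were about 8 to 23 with 43 per arm, instead of 84.

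A partially nested mixed model fitted by REML (43 per arm) gave 3.3-5.1%. It estimated the group variance as exactly zero in 27-60% of trials.

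**Step 4: what the repair costs (group means, near-equal groups).**

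| | ICC 0 | ICC 0.05 | ICC 0.10 |
|---|---|---|---|
| Interval widening, 43 per arm | 4-10% | 12-27% | 19-43% |
| Interval widening, 34 per arm | 4-10% | 10-23% | 15-36% |
| Power at d 0.61, 43 per arm (unclustered at ICC 0: 80%) | 72-76% | 60-71% | 52-66% |
| Power at d 0.61, 34 per arm (unclustered at ICC 0: 70%) | 62-66% | 53-62% | 47-58% |

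Unequal groups cost more. With 34 analysed per arm and illustrative sizes 12/10/7/5 or 9/8/7/4/3/3, intervals at ICC 0 are about 12-14% wider.

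**The case against.** **The plan is silent, not wrong.** A reader might infer that the plan has chosen an unclustered test such as an independent t-test. It has not. It says that changes will be compared and names no test, so a model with a group term is neither specified nor excluded. This stands: the point is an omission, and the error rates describe what happens if the comparison is run without a group term.

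**Nor is it the only analysis stated.** Mediation is also planned. The change comparison is the only stated effectiveness analysis.

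**Every magnitude is assumed.** This also stands. The ICC, number of groups, allocation ratio and 34 per arm are illustrations; planning interviews with drop-outs shows only that drop-out is expected. At ICC 0 there is no harm and at 0.01 very little. The figures near 10% lie at the top of the assumed range.

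**The fix costs power even when clustering is negligible.** True. At ICC 0.01 with 43 per arm, power at d 0.61 falls from about 79% to 69-75%, for a small gain in type I error. Part of the loss at higher ICC is a real consequence of clustering: with a correct standard error and no small-sample penalty, groups of 8 at ICC 0.05 would already bring 80% down to about 73%. The rest is the price of having few groups. Adjusting only if the estimated ICC looks large is no way out, because 4 to 7 groups cannot estimate it well.

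**Group means against mixed model is a matter of preference.** Accepted; either will do.

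**Conclusion.** The point holds as an omission that should be fixed. The text establishes individual randomisation, group delivery in one arm only, and an effectiveness comparison with no model or therapy-group term. The direction of the error is certain if that comparison is run unclustered and outcomes correlate positively within CA-CBI groups.

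Its size is not certain. Under the assumptions listed, it ranges from nothing at ICC 0 to roughly double the nominal error rate with 4 groups at ICC 0.10.

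Two stronger readings are not supported. The first is that 86 participants are too few: the documents give no target effect or power, so this cannot be judged, and the missing basis for 86 is a separate gap in reporting that adds no weight here. The second is that two facilitators lead all the groups: the plan says only that two will be interviewed. If facilitators do lead several groups, that further correlation is not covered by these figures and cannot be sized from the documents.

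**What to change.** 1. Record a therapy-group ID for each CA-CBI participant at assignment, keep it for those who drop out, and record the facilitator. State the planned group size and number of groups.
2. Prespecify, for K10 and each secondary outcome, one analysis that allows for therapy group in the CA-CBI arm only, to be used whatever the estimated ICC. Either of these is acceptable:
   - mean change per CA-CBI group against individual ETAU changes, with Satterthwaite degrees of freedom. This keeps the change-score comparison and needs no rule for a zero group variance, but it weights groups and not people if sizes differ;
   - a partially nested mixed model with a random group effect in CA-CBI only, arm-specific residual variance and small-sample degrees of freedom. The rule for a zero group-variance estimate, including its degrees of freedom, must be written down first.
3. For the exploratory mediation models, use an individual-level method that allows for therapy group, for example a random group effect in CA-CBI only. Group means do not carry over to the mediator-to-outcome path.

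The change needs one or two ID variables, some analysis wording and no extra participants. The statistical price of group means is set out in step 4 of the working. With the mixed model and 43 per arm, intervals are about 8-15%, 14-31% and 20-46% wider at ICC 0, 0.05 and 0.10, and the test is conservative at low ICC. The cost of the mediation adjustment was not calculated.

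### The post-test is collected to test effectiveness, but no stated analysis uses it to estimate the end-of-treatment effect or to show whether a follow-up effect was held, fading or delayed

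*Combined protocol and SAP*

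**What the plan says.** All statements are in The Study Protocol.

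- **Overview paragraph, schedule.** "To test the effectiveness of CA-CBI, all participants will be assessed one week before the intervention (pre-test), one week after the intervention (post-test), and one". The quote is cut there; the third assessment is the follow-up, a month later than the post-test.
- **Overview paragraph, primary outcome.** "The primary outcome is the psychological distress at the follow-up phase".
- **Second stage, post-test.** "In order to test the effectiveness of the CA-CBI for COVID-19 survivors, post-test assessment will be conducted with participants in the intervention and control group". This visit falls a week after treatment ends.
- **Second stage, follow-up.** "To be able to observe the long-term effects of the CA-CBI, follow-up assessment will be conducted one month after the post-test".
- **Data analysis paragraph.** "The effectiveness of the intervention will be tested by comparing the changes in the scores of primary outcome measure (K10) and secondary outcome measures". The change is taken "between the baseline and follow-up measure". The secondary measures listed are PHQ-9, GAD-7, PCL-5, SCL-90-R Somatization and WHOQOL-BREF.
- **Data analysis paragraph, the only other quantitative analysis.** "Mediation analyses will be conducted to explore the mechanisms of change by using the Psychological Flexibility Scale and Emotion Regulation Questionnaire". No time points are named.

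**The concern.** The second-stage text gives the post-test an effectiveness role in both arms, yet the one comparison that the analysis paragraph describes leaves that visit out. A full assessment would be collected for a purpose with no planned analysis.

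Three things are at stake:

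1. **The end-of-treatment effect has no pre-specified estimate.** If CA-CBI works at the end of treatment and the effect has gone a month later, the stated analysis shows only the absence of a difference at follow-up.
2. **A later post-test analysis would be post hoc.** With six outcome measures and two post-randomisation visits, leaving the visit open allows the choice of time point to follow the results.
3. **Information may be lost.** A change from baseline to follow-up needs a follow-up score, and no missing-data method is stated. Taken literally, a participant with a post-test but no follow-up adds nothing to the comparison.

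**Working it through.** **1. Purpose against analysis**

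| Visit | Stated purpose (second stage) | Stated effectiveness analysis |
|---|---|---|
| Post-test | test effectiveness, both arms | none |
| Follow-up | longer-term effects; primary time point | change from baseline, K10 and five secondary measures |

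The mediation sentence does not fill the empty cell. It concerns mechanisms, names no visits and defines no effectiveness contrast.

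**2. What one contrast can show**

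Let D_P and D_F be the arm differences at post-test and follow-up. The stated analysis estimates D_F only. The same D_F is compatible with D_P = D_F (held), D_P larger than D_F (fading) and D_P smaller than D_F (delayed). Telling these apart needs D_P. Establishing that an effect exists at follow-up does not.

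**3. Efficiency**

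The documents give no figure to reproduce here, and both inputs are assumptions:
- m, the share of participants with a post-test but no follow-up: 0.1 to 0.3
- rho, the post-test/follow-up correlation given baseline: 0.4 to 0.7

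Assume everyone has a post-test and that missingness depends only on observed data. Relative to follow-up completers only, the variance ratio is

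rho²(1 − m) + (1 − rho²) = 1 − m·rho²

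- m = 0.1, rho = 0.4: 1 − 0.1 × 0.16 = 0.984
- m = 0.2, rho = 0.6: 1 − 0.2 × 0.36 = 0.928
- m = 0.3, rho = 0.7: 1 − 0.3 × 0.49 = 0.853

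The variance falls by about 2% to 15%. In the middle case the standard error falls by 1 − √0.928, about 3.7%.

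For a given share missing follow-up, the gain is smaller if some of them also missed the post-test. Suppose 20% miss follow-up and only half of these gave a post-test. Among those with at least one score, m becomes 0.10/0.90 = 0.111, and the ratio is 1 − 0.111 × 0.36 = 0.960.

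**4. Precision of the change between visits**

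The total is stated ("The required sample is identified as 86 participants for this stage"). The documents give no inputs behind it, so it cannot be re-derived. Assume 1:1 allocation (43 per arm), no dropout, two-sided 0.05 and 80% power (multiplier 1.96 + 0.84 = 2.80).

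- Arm difference at one visit: 2.80 × √(2/43) = 0.60 SD
- Change in arm difference, rho = 0.4: 2.80 × √((2/43) × 2 × 0.6) = 0.66 residual SD
- Change in arm difference, rho = 0.7: 2.80 × √((2/43) × 2 × 0.3) = 0.47 residual SD

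The trial could detect only a change between visits of about the same order as the main effect it could detect. A non-significant change would therefore not establish maintenance.

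**5. Effect on the primary test**

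If the post-test were a second co-equal test at 0.05, the family-wise error could reach 0.10 (1 − 0.95² = 0.0975 if independent). Splitting alpha to 0.025 each would raise the detectable difference from 0.60 to about 0.67. Keeping the post-test secondary avoids both, and the 86 need not change on this account.

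**The case against.** The strongest reply is that nothing is inconsistent where it matters most. Follow-up is the declared primary time point, and the stated comparison ends there. If an effect has faded by then, finding no difference is the right answer to the declared question. This stands, and it limits the point to secondary questions and efficiency.

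Four stronger readings are tempting, and the documents do not support them:

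- **That the post-test will never be analysed.** The plan states one comparison and excludes none. The mediation analysis may use post-test data.
- **That the trial could say nothing about lasting effects.** A randomised difference at follow-up is evidence of an effect one month after the post-test. Only the course over time is missing.
- **That each visit has an exclusive job.** The overview paragraph ties all three assessments to effectiveness. This softens the contrast in the second-stage text, but it also makes the absence of any post-test analysis harder to explain.
- **That the five drop-outs to be interviewed show follow-up data will be lost.** They are asked about barriers to attending sessions. Nothing says that they miss assessments.

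It can also be said that one sentence naming the post-test as a secondary time point would do, and that a joint model is a preference. A sentence would close the reporting gap. It would not keep participants with only a post-test in the follow-up estimate, which the joint model does at little cost.

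**Conclusion.** The point holds as a gap in secondary analyses: the post-test has a stated effectiveness purpose and no stated effectiveness analysis, for K10 and all five listed secondary measures. This rests on the text alone and needs no assumed figure. A reader might infer that the primary analysis is wrong or contradicts its endpoint. It does not.

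The efficiency loss is modest, about 2-15% of the variance of the follow-up estimate, and depends on the assumed missingness and correlation. It is a supporting reason. The main reason is that the end-of-treatment effect should be defined before data are seen. The plan should be changed on this point, but the validity of the primary test does not depend on it.

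**What to change.** - **Primary.** Keep K10 at follow-up as the single primary test. Estimate the arm difference from a baseline-adjusted repeated-measures (mixed) model containing post-test and follow-up scores and an arm-by-visit term, including everyone with at least one post-randomisation score.
- **Secondary.** Name the post-test arm difference from the same model as the end-of-treatment result.
- **Descriptive.** Report the change in arm difference from post-test to follow-up with a confidence interval, and state that a non-significant change does not establish maintenance.
- **Other measures.** Use the same model for PHQ-9, GAD-7, PCL-5, SCL-90-R Somatization and WHOQOL-BREF.

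**Cost.** Revised analysis wording and a little more analysis work, which the planned SPSS 26.0 can handle. No new data, visits or participants are needed. The downside is two extra contrasts per outcome, 2 × 6 = 12 across the listed measures. They should be labelled secondary or exploratory so that they do not compete with the primary test.

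### The only stated K10 comparison needs a follow-up value, and no analysis set or missing-data method is given, so a completers-only primary analysis, biased in an unknown direction, is not ruled out

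*Combined protocol and SAP*

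**What the plan says.** All statements are in The Study Protocol.

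- **Primary outcome (overview paragraph):** "The primary outcome is the psychological distress at the follow-up phase".
- **Assessments (overview paragraph):** "all participants will be assessed one week before the intervention (pre-test), one week after the intervention (post-test), and one month after the post-test (follow-up"). The second-stage paragraph confirms that the post-test is taken in both arms.
- **Effectiveness test (data analysis paragraph):** "The effectiveness of the intervention will be tested by comparing the changes in the scores of primary outcome measure (K10"), together with the secondary measures, "between the baseline and follow-up measure". This is the only sentence on how effectiveness is tested. The post-test is not in it. SPSS 26.0 is named, but no test or model.
- **Drop-outs (third stage, process evaluation):** "Interviews will be conducted with 5 completers, 5 drop-outs and 2 facilitators". The stated purpose is to learn what helped or hindered attending and delivering the sessions.
- **Not stated:** analysis set, handling of missing K10 scores, sensitivity analysis, expected loss in either arm, and allocation ratio.

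**The concern.** A change from baseline to follow-up can be computed only for someone with a follow-up K10. If the sentence is carried out literally, the primary comparison is made among those who return the last survey, not among those randomised. A participant with pre-test and post-test scores but no follow-up gets zero weight, although the post-test says much about where that person was heading.

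Unequal loss is plausible because the arms ask for different things. CA-CBI means 8 weeks of online group sessions. ETAU means brief psychoeducation and a referral list, with CA-CBI available once all measures are done, which is itself a reason to stay. If those who leave CA-CBI differ in outcome from those who stay, the primary result is shifted, and recruiting more people would not remove the shift. With no rule written down, the analysis set and missing-data method could also be chosen after the data are seen.

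**Working it through.** **1. The plan's own figure.** The required sample is 86. Its inputs are not given, so it cannot be reproduced, and one cannot tell whether it allows for loss. Two assumed sets, both two-sided 5% and 1:1, reach it:
- Effect 0.70 SD, 90% power, no loss: 2(1.960 + 1.282)²/0.70² = 42.9, so 43 per arm and 86 in total.
- Effect 0.65 SD, 80% power, 10% loss: 2(1.960 + 0.842)²/0.65² = 37.2, so 38 per arm; 38/0.9 = 42.2, so 43 per arm and 86 in total.

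Nothing here shows 86 to be wrong. The steps below assume 43 per arm.

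**2. Size of a completers-only bias.** Let *p* be the share of CA-CBI without follow-up. Let *g* be the amount by which their mean change is worse than that of the CA-CBI participants observed, in SDs of change. Take ETAU as complete and the true effect as zero. The whole-arm mean improvement is (1 − p)m + p(m − g) = m − pg, where m is the observed mean, so the bias is **p × g**. The SE is √(1/43 + 1/(43(1 − p))), and the chance of a significant result favouring CA-CBI is Φ(pg/SE − 1.96), nominally 2.5%.

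With K10 SD 7 and pre-to-follow-up correlation 0.5 (both assumed), the SD of change is 7√(2(1 − 0.5)) = 7 points.

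| CA-CBI missing | g (SD) | Bias (SD) | Bias (K10 points) | P(significant, favours CA-CBI) |
|---|---|---|---|---|
| 5/43 (12%) | 0.5 | 0.058 | 0.4 | 4.5% |
| 9/43 (21%) | 0.5 | 0.105 | 0.7 | 6.6% |
| 9/43 (21%) | 1.0 | 0.209 | 1.5 | 14.7% |
| 13/43 (30%) | 0.5 | 0.151 | 1.1 | 9.3% |
| 9/43 (21%) | −0.5 | −0.105 | −0.7 | 0.8% |

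Worked row (9/43, g = 0.5): SE = √(1/43 + 1/34) = 0.2295; 0.105/0.2295 = 0.456; Φ(0.456 − 1.96) = 0.066. The last row has the better-off participants leaving, and the sign reverses.

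**3. Simulation with the post-test included.** Assumptions: no true effect; SD 7; correlations 0.6 (pre-post), 0.5 (pre-follow-up) and 0.7 (post-follow-up); 25-30% of CA-CBI without follow-up, with log-odds of loss changing by 0.7 to 1.5 per SD of post-test change; ETAU complete or 10% missing at random.
- Completers-only change, non-improvers leaving: bias of about 0.7 to 1.5 points favouring CA-CBI. With 43 per arm and 10% random loss in ETAU, false positives favouring CA-CBI are about 6-13% against 2.5%.
- Completers-only change, improvers leaving: about 0.7 to 1.5 points against CA-CBI.
- Likelihood estimate using all three surveys, post-test observed: bias at most 0.05 points.
- Same loss, but the post-test missing as well: 0.5 to 1.1 points remain, about two-thirds of the completers-only bias.
- Loss driven by the unseen follow-up change: 0.6 to 1.3 points remain if the post-test is observed, 0.9 to 1.8 if it is not.

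In every scenario the likelihood estimate was less biased than the completers-only change.

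**The case against.** The strongest reply is that the plan is silent rather than wrong. Comparing changes describes a contrast, and a mixed model on three surveys or multiple imputation could estimate it too. That stands: no completers-only analysis is stated. But either method has to be read into a sentence that mentions two time points and no model.

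A reader might infer that the drop-outs the plan expects will leave the primary comparison. The documents do not support this. Those drop-outs are to be interviewed about attending sessions, the K10 is an online survey that can be returned without attending, and the overview intends all participants to be assessed at all three times. Still, an intention to measure does not say who is analysed when a survey is not returned.

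A reader might also infer that the result will be biased towards CA-CBI. The documents give no loss by arm and no outcome difference between leavers and stayers, and reversing the selection reverses the sign.

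Finally, the near-zero bias of the likelihood estimate depends on a favourable case, in which the post-test is always seen and drives the loss. People who leave during the 8 weeks may miss the post-test as well. The choice of model is also partly preference: another pre-specified method, such as multiple imputation with sensitivity analyses, would close the gap.

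**Conclusion.** The point holds as a gap in the primary analysis. The one effectiveness comparison uses baseline and follow-up only, and neither an analysis set nor a missing-data method is stated. As written, participants without a follow-up K10 drop out of the comparison even when their post-test is available. Bias arises if loss is related to outcome and differs by arm. Its direction is not determined by the documents, and its size, about 0.7 to 1.5 K10 points (0.10 to 0.21 SD), rests on assumed SD, correlations, loss rates and loss mechanism. The case for acting rests on the omission and on how little the repair costs, not on a demonstrated bias towards CA-CBI.

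**What to change.** Replace the analysis sentence with a short specification:

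1. All randomised participants are analysed in their allocated arm.
2. The arm difference in K10 at follow-up is estimated from a likelihood-based repeated-measures model (for example SPSS MIXED, in the software already named) fitted to pre-test, post-test and follow-up, so that a person with a post-test but no follow-up still contributes.
3. The post-test and follow-up surveys are sent to participants who stop attending sessions. The overview implies this; it should be explicit.
4. Missing follow-up is reported by arm.
5. A missing-not-at-random sensitivity analysis is added, for example with CA-CBI participants without follow-up assumed to be at their pre-test K10. It is needed because the model in item 2 does not remove bias when the post-test is also missing or loss depends on the unseen follow-up score.

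This is a cheap improvement: a few sentences and a little more analysis work, with no new surveys, visits or participants. Precision does not suffer: in the simulation the SD of the estimate was 1.59 to 1.70 points with the likelihood model and 1.65 to 1.71 with the change score. The downside is that the estimated effect may be smaller than among completers. The specification should be fixed before outcome data are seen.
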